- pro-inflammatory changes in mice and monkeys after up to 26 and 39 weeks of treatment, respectively, included slight increases in liver weights (up to ~1.6- and up to ~2.1-fold over control) mainly at \geq 6 and \geq 12 mg/kg/wk in mice and monkeys, respectively. Increased spleen weights (up to ~1.9- and up to ~2.5-fold over control) were also observed mainly at \geq 6 and \geq 12 mg/kg/wk in mice and monkeys, respectively. In mice, increased MCP-1 (up to 7.7-fold over control) was accompanied by splenomegaly and multi-organ vacuolated/granular macrophage infiltrates in the 20 mg/kg/wk dose group.
- in monkeys, sporadic incidences of minimal to marked mononuclear cell infiltration at injection site skin were seen in all dose groups.

The most noteworthy finding in the monkey study was a marked PLT reduction, which occurred in one male monkey at the mid-high dose level, 12 mg/kg/wk (840 mg/wk HED). At Day 65, this animal presented with petechia and oral mucosal bleeding with a PLT count of $8 \times 10^3/\mu\text{L}$. This animal was treated with methylprednisolone on Days 65 and 72, and the PLT count quickly recovered to $145 \times 10^3/\mu\text{L}$ on Day 70. This animal continued treatment with ISIS 678354, without a dosing holiday, until scheduled necropsy on Day 93 (interim) with the last clinical pathology evaluation on Day 93 again showing a marked reduction in PLT count ($6 \times 10^3/\mu\text{L}$). Marked PLT reductions were not observed in the 30 mg/kg/wk dose group (2100 mg/wk HED) for up to 13 weeks or in any of the remaining dose groups for up to 39 weeks.

In vivo safety pharmacology and *in vitro* genetic toxicity studies indicate that ISIS 678354:

- had no effects on cardiovascular (blood pressure [BP], heart rate [HR], electrocardiogram [ECG]), respiratory (respiration rate, arterial blood gases), or central nervous system (CNS) parameters in the monkey consistent with previous experience with 2'-MOE ASOs (Kim et al. 2014).
- was not genotoxic and did not increase the rate of mutations in the *in vitro* bacterial reverse mutation assay nor induce chromosomal abnormalities in mammalian cells

Taken together, these data support the evaluation of ISIS 678354 as a potential new therapeutic approach to reduce hepatic apoC-III expression in patients with elevated TGs to reduce triglycerides, potentially improve their insulin sensitivity and reduce CVD risk.

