8.6.3 Stopping Rule for Platelet Count Results

Actions to be taken in the event of a low platelet count are summarized in Table 3 below.

In the event of any platelet count less than $50,000/\text{mm}^3$, or a platelet count less than $75,000/\text{mm}^3$ that occurs while the patient is already on reduced dose, dosing of the patient with Study Drug will be stopped permanently (Table 3). Platelet count will be monitored daily until 2 successive values show improvement then monitored every 2-3 days until platelet count is stable.

Administration of glucocorticoids is recommended for patients whose platelet count is less than $25,000/\text{mm}^3$. Recovery in platelet count may be accelerated by administration of high dose glucocorticoids. Treatment guidelines for immune thrombocytopenia ([Provan et al. 2010](#)) recommend Dexamethasone 40 mg daily for 4 days every 2-4 weeks for 1-4 cycles; Prednis(ol)one 0.52 mg/kg/d for 2-4 weeks then taper; or methylprednisolone 30 mg/kg/day for 7 days (note: may require continuation with oral glucocorticoids after methylprednisolone).

In the event of a platelet count $< 75,000/\text{mm}^3$ and $\geq 50,000/\text{mm}^3$, and in the absence of major bleeding or clinically-relevant non-major bleeding (defined below; [Büller et al. 2007](#)), dosing of a patient with Study Drug should be suspended temporarily until the platelet count has recovered to $\geq 100,000/\text{mm}^3$. If dosing is continued, it must be at a reduced dose as shown in Table 3. The

suitability of the patient for continued dosing will be determined by the Investigator in consultation with the Study Medical Monitor and will be based on factors such as the original rate of decline in the patient's platelet count, whether any bleeding events were experienced by the patient, and the speed of recovery of platelet count after interruption of dosing.

If, after reintroduction of Study Drug, the platelet count again falls below 75,000/mm³, then dosing of the patient with Study Drug will be stopped permanently.

Once a patient commences weekly monitoring this frequency of monitoring should continue until the platelet count returns to the normal range ($\geq 140K/mm^3$) for 2 successive values.

Any unreportable platelet count result must be rechecked and determined not to have met a stopping rule before dosing can continue.

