A confirmed laboratory value is based on consecutive lab values performed on a different day to, but within 7 days (no matter central lab data or local lab data). If consecutive value is same or worse, then the initial value is confirmed. If the consecutive value is better, then the initial value is confirmed using consecutive value. If there is no retest within 7 days, then the initial value is presumed

confirmed. If there are multiple results on the same day (no matter central lab data or local lab data), then the worst value will be utilized in the analysis.

The following lab results will be graded based on Toxicity Grading Scale for Healthy Adult and Adolescent Volunteers Enrolled in Preventive Vaccine Clinical Trials (September 2007). Number and proportion of patients with shift from baseline to worst post-baseline values by toxicity grade will be tabulated for on-treatment and on-study periods. Post-baseline lab results are defined as any assessment taken after the first dose no matter central lab or local lab data. If a patient has no baseline value but has a post-baseline value, then the baseline assessment will be labeled as “unknown”. Likewise, if a patient has a baseline value but has no post-baseline value, then the worst value will be labeled as “unknown”. Shift tables for eGFR, ALT, AST and total bilirubin will be provided using original and confirmed values.

- Hemoglobin: shift from Baseline to minimum post-baseline value
- WBCs: shift from Baseline to minimum post-baseline value
- Platelets: shift from Baseline to minimum post-baseline value
- BUN: shift from Baseline to maximum post baseline value
- Creatinine: shift from Baseline to maximum post-baseline value
- eGFR: shift from Baseline to minimum post-baseline value
- Proteinuria: shift from Baseline to worst post-baseline value
- ALT: shift from Baseline to maximum post-baseline value
- AST: shift from Baseline to maximum post-baseline value
- Alkaline phosphatase: shift from Baseline to maximum post-baseline value
- Total bilirubin: shift from Baseline to maximum post-baseline value

eGFR will be graded using the following criteria:

- $\geq 90 \text{ mL/min}/1.73\text{m}^2$
- $\geq 60 \text{ mL/min}/1.73\text{m}^2$ to $< 90 \text{ mL/min}/1.73\text{m}^2$
- $\geq 30 \text{ mL/min}/1.73\text{m}^2$ to $< 60 \text{ mL/min}/1.73\text{m}^2$
- $\geq 15 \text{ mL/min}/1.73\text{m}^2$ to $< 30 \text{ mL/min}/1.73\text{m}^2$
- $< 15 \text{ mL/min}/1.73\text{m}^2$

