Abnormalities of platelet counts: The number and percentage of patients falling in each of the following categories (using available central and local laboratory assessments) based on worst post-baseline assessments will be provided:

- Any 2 occurrences of platelet count < 140,000 cells/mm³
- Any single occurrence of platelet count < 100,000 cells/mm³
- Any 2 occurrences of platelet count < 140,000 cells/mm³ or any single occurrence of value < 100,000 cells/mm³

The nadir platelet count will be summarized by following categories:

- Decrease \geq 30% from baseline
- Decrease \geq 50% from baseline
- 100,000 cells/mm³ to < 140,000 cells/mm³
- 75,000 cells/mm³ to < 100,000 cells/mm³
- 50,000 cells/mm³ to < 75,000 cells/mm³
- 25,000 cells/mm³ to < 50,000 cells/mm³
- 0 to < 25,000 cells/mm³

All categories of abnormalities in platelet count will be summarized based on confirmed values for on-study period as well.

Abnormalities of renal function: The number and percentage of patients falling in each of the following categories (using available central and local laboratory assessments) based on confirmed worst post-baseline assessments will be provided:

- eGFR by CKD-EPI $>$ 25% decrease from baseline
- UACR $>$ 250 mg/g
- UPCR $>$ 0.5 g/g
- Serum creatinine increase of $>$ 0.3 mg/dL from baseline

3.7.5 12-Lead Electrocardiogram

ECGs will be performed in triplicate at the visits indicated in the Protocol Appendix A. Patients in PK Subgroup will have additional ECG conducted during the treatment period. Patients determined to have a pacemaker rhythm will be excluded from summary tables.

The ECG data include ventricular rate, PR interval, QRS duration, QT and corrected QT intervals. For the continuous variables, the average of measurements at a given visit will be used for analysis. For the continuous variables above, descriptive statistics (n, mean, standard error, standard deviation, median, P25, P75, minimum, maximum, and mean 95% CI) of the observed values, as well as the change from baseline to each nominal study visit, will be presented by treatment group and for pooled placebo in summary tables. The summary table will be presented in SS and in PK Subgroup separately. Scheduled visits will be used for all summary tables.

The number and percent of patients who have the following reported events will be tabulated by treatment group and for pooled ISIS 678354.

- Absolute QT/QTcF/QTcB $>$ 450 msec
- Absolute QT/QTcF/QTcB $>$ 480 msec

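### The SAP's confirmed-value rule lets a platelet repeat drawn after glucocorticoids replace a true severe count in the supplementary confirmed platelet table

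*Combined protocol and SAP*

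**What the plan says.** SAP 3.7.4 sets the rule for all analytes: "A confirmed laboratory value is based on consecutive lab values performed on a different day to, but within 7 days", with central and local results treated alike. Three cases follow.

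- Repeat no better: "If consecutive value is same or worse, then the initial value is confirmed".
- Repeat better: "If the consecutive value is better, then the initial value is confirmed using consecutive value". No minimum improvement is required, and no repeat is excluded because of treatment given in between.
- No repeat: "If there is no retest within 7 days, then the initial value is presumed" confirmed.

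Under the platelet heading of the same section, the category and nadir tables are first built on worst unconfirmed counts, for the on-treatment and on-study periods. Then: "All categories of abnormalities in platelet count will be summarized based on confirmed values for on-study period as well".

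Protocol 8.6.3 and Table 3 require daily counts below 50,000/mm³ until two successive values improve, and recommend glucocorticoids below 25,000/mm³. Protocol 8.6.3 adds: "Recovery in platelet count may be accelerated by administration of high dose glucocorticoids".

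**The concern.** Confirmation asks whether the first result was real. A better repeat answers that question only if nothing was done to raise the count in between. For platelets below 25,000/mm³ the protocol recommends treatment meant to raise the count, so the next count may show response to treatment and not laboratory error. The SAP handles both cases alike and gives the patient the recovered value.

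The rule is also uneven. A patient who is treated and retested promptly can lose the severe band, while a patient with the same count and no retest keeps it.

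Platelet reductions are a listed safety endpoint (Protocol 10.1.3) and their incidence enters dose selection (Protocol 10.1.4). Each cohort has about 25 × 4/5 = 20 patients on active drug, so one downgraded patient changes that row of the confirmed table by 1/20 = 5 percentage points. Because the change comes from successful treatment of a low count, it makes the affected arm look safer.

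**Working it through.** The plan states no figure on this point, so there is nothing to reproduce. The check applies the SAP rule to platelet courses.

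**Inputs**
- Rule and 7-day window: SAP 3.7.4.
- Bands (×10³/mm³): 0 to <25, 25 to <50, 50 to <75, 75 to <100, 100 to <140: SAP 3.7.4.
- Sampling and treatment after a low count: Protocol 8.6.3 and Table 3.
- The only platelet course with figures in the documents is one monkey in Protocol 2.3.3: 8 × 10³/µL on Day 65 with petechiae and oral mucosal bleeding. "This animal was treated with methylprednisolone on Days 65 and 72, and the PLT count quickly recovered to" 145 × 10³/µL on Day 70. On Day 93 the count was 6 × 10³/µL, with dosing continued throughout.

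**Formula.** For counts v₁, v₂, … on different days, confirmed value cᵢ = max(vᵢ, vᵢ₊₁) if the next count is within 7 days, otherwise cᵢ = vᵢ. The patient's worst confirmed value is the minimum of the cᵢ.

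**Step 1: the printed pair.** 8 then 145 after 5 days: c = max(8, 145) = 145. The count moves from the lowest band to outside every absolute low band. It could still count as a fall of at least 30% if baseline was at least 145/0.7 ≈ 207; no baseline is given.

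**Step 2: the same recovery sampled earlier.** The path between the two counts is not reported, so two are assumed. Straight line: (145 − 8)/5 = 27.4 per day. Geometric: (145/8)^(1/5) ≈ 1.785-fold per day.

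| First repeat | Confirmed, straight line | Confirmed, geometric |
|---|---|---|
| Day 1 | 35.4 (25 to <50) | 14.3 (<25, unchanged) |
| Day 2 | 62.8 (50 to <75) | 25.5 (25 to <50) |
| Day 3 | 90.2 (75 to <100) | 45.5 (25 to <50) |
| Day 5 | 145 (≥140) | 145 (≥140) |

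The protocol's daily schedule corresponds to the first row.

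**Step 3: how large a next-day rise changes the band.** To reach 25, a count of 8 must rise 25/8 ≈ 3.1-fold, 15 must rise 1.67-fold, 20 must rise 1.25-fold and 24 must rise 1.04-fold. Counts just under a boundary are the easiest to move.

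**Step 4: assumed courses (×10³/mm³)**
- 22, then 40 next day: confirmed 40; <25 becomes 25 to <50.
- 20, 18, 60 on consecutive days: the first value is kept at 20 because the next count is worse. Worst confirmed is 20, still <25.
- 45, 44, 55 on consecutive days: worst confirmed 45, band unchanged.
- 45 with no retest for 8 days: 45 stands.
- 45, then 55 next day: confirmed 55; 25 to <50 becomes 50 to <75. This belongs to the point only if platelet-directed treatment was given, which the protocol does not recommend as routine in that band.

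**Step 5: after the fix.** If treatment came between the counts, 8 then 145 stays at 8 and 22 then 40 stays at 22, both <25.

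**The case against.** The strongest reply is that this is one added table. The same categories and the nadir bands are reported on unconfirmed worst counts for both periods. The platelet shift table uses the minimum post-baseline count, all results are listed, and patients stopped under a stopping rule are tabulated. Bleeding events have their own summary. The SAP also leans towards the low value in two places: the worst same-day result is used, and an unretested value stands. All of this is correct and limits the point to the confirmed table.

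A second reply is that daily sampling protects against the error: a low count that persists to the next day in the same band keeps that band. That also stands, and the geometric path in the working shows no downgrade under daily counts.

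A reader might infer that the monkey's thrombocytopenia would vanish under the rule. It would not. The Day 93 count of 6 has no reported retest within 7 days, so it is presumed confirmed and the animal remains in the lowest band. Only the first episode is downgraded. In the trial, however, a patient below 50,000/mm³ is to stop permanently under Protocol 8.6.3, so a second episode may not occur to restore the grade.

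These replies do not remove the defect. A table headed as confirmed that omits an event shown in the unconfirmed table can be read as evidence of artefact, when the repeat cannot show that.

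**Conclusion.** The point holds for the confirmed platelet table only. The rule can downgrade a true severe count when platelet-directed treatment comes before the very next count and that count lies in a better band. The size runs from no change to loss of every absolute low band, depending on when the repeat is drawn and how fast the count recovers. The recovery paths are assumptions fitted to two counts in one steroid-treated animal.

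Three stronger readings are not supported:

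- That any better count within 7 days replaces the low one. The SAP uses the consecutive count only.
- That the patient loses special-interest status. That follows from the protocol's definition (below 50,000/mm³) and its expedited reporting, which an SAP table does not alter.
- That drug withdrawal alone produces the same bias. No passage says that a dose hold raises platelets within a few days, and the monkey was dosed without a break.

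Separately, the protocol differs with itself on confirmation. The stopping-rule guidance in Protocol 8.5 requires criteria in 8.6.1 to 8.6.3 to be met and confirmed before permanent discontinuation, whereas 8.6.3 acts on any count below 50,000/mm³. These passages must be reconciled.

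**What to change.** This is a change to the analysis only. In SAP 3.7.4:

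1. State that, for platelets, a repeat drawn after glucocorticoid, transfusion or other platelet-directed treatment cannot replace the earlier count, unless the first specimen was clumped or otherwise unreportable.
2. State that the unconfirmed nadir is the basis for platelet severity.
3. Footnote the confirmed table to say so.

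Do not extend the bar to repeats drawn after a dose hold or stop. Dosing is paused or stopped for every count below 75,000/mm³, so confirmed and unconfirmed values would be nearly identical there and the table would lose its purpose.

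The cost is a few sentences and a date condition in programming. Concomitant treatments and dates are already recorded in the eCRF. The SAP should add a convention for a repeat drawn on the calendar day treatment starts, where dates alone do not give the order. The downside is that an occasional spurious low count that was treated stays as confirmed; it can be footnoted.

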6.2 Additional Study Assessments

6.2.1 Laboratory Assessments

Laboratory analyte samples will be collected throughout the study as per the Schedule of Procedures in [Appendix A](#). A list of these analytes is contained in [Appendix B](#).

Routine blood chemistry and urine samples should be taken after fasting for at least 10 hours and preferably not more than 12 hours. Any confirmatory test, or test taken for safety reasons, may be taken at any time, irrespective of fasting status, but no later than 7 days after the initial result is obtained. During preparation for fasting samples, the patient can drink water and they should ensure that they consume sufficient water in order to not become dehydrated.

If tests are uninterpretable (e.g., due to clumping, hemolysis or quantity not sufficient) or missing, a repeat blood or urine specimen should be re-drawn as soon as possible (ideally within 1 week).

While on treatment, hematology samples will be collected every 14 days (± 2 days). Each time a hematology lab is drawn and sent to the central laboratory for analysis, an additional sample should be collected in parallel and analyzed locally. In the event that both the central and local samples are unreportable (e.g., due to hemolyzed or clumped blood samples), patient dosing cannot continue until another sample is repeated and determined not to have met a platelet stopping rule.

If there is no reportable platelet count within 14 days of the last platelet count, the Investigator will contact the patient to hold dosing until a new platelet count is obtained and reviewed.

While on treatment blood and urine samples for renal function testing will also be collected every 14 days (± 2 days) and sent to the central laboratory for analysis for the first 3 months of the study treatment, and monthly thereafter during the Treatment Period per [Section 8.5.2](#).

While on treatment liver function testing will also be collected every 14 days (± 2 days) and sent to the central laboratory for analysis for the first 3 months of the study treatment, and monthly thereafter during the Treatment Period per [Section 8.5.1](#).

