All lab samples are to be sent to the central laboratory by overnight courier and processed. Lab Alerts issued as per protocol safety monitoring requirements or stopping rules will indicate the applicable protocol section to facilitate review and will be immediately and simultaneously sent by email to the Investigator, the Sponsor and the CRO Medical Monitors, the Sponsor Drug Safety Physician, and the Clinical Trial Manager (CTM), and should be received by them within 2 days from sample collection. Hematology results from the site's local laboratories are received by the study center staff per the local laboratories' standard reporting time, and should be entered as soon as possible into the eCRF to inform the Sponsor and CRO study monitoring teams.

All platelet count results must be reviewed promptly (within 48 hours of receipt) by the Investigator, or designee, to ensure that the count has not met the stopping rule and to determine whether the rate of decline is suggestive that the patient could be approaching the dose interruption rule of 75,000/mm³ as specified in [Section 8.6.3](#). Any case of a platelet count reduction to levels below 50,000/mm³ is considered an adverse event of special interest and must be reported in an expedited fashion to the Sponsor as per [Sections 9.3.3.1](#) and [9.4.1](#).

All liver and renal function tests must also be reviewed promptly (within 48 hours of receipt) by the Investigator, or designee, to ensure that the result has not met the stopping rule. Any event meeting renal stopping rules criteria described in [Section 8.6.2](#) is considered an adverse event of special interest and must be reported in an expedited fashion to the Sponsor as per [Sections 9.3.3.1](#) and [9.4.1](#).

All lab alerts received, including those related to platelet, liver, or renal function monitoring/stopping rules, are also reviewed promptly by the Sponsor and the CRO Medical Monitors who will agree on actions to be taken. Within 24 hours of receiving an actionable lab alert the CRO Medical Monitor will communicate instructions to the Investigator and the study personnel by emailing them the Safety Surveillance Form that needs to be completed and signed by the Investigator/study personnel and promptly returned to the Sponsor and CRO Medical Monitor. In urgent cases, such as platelets results below 50,000/mm³, or liver or renal test results reaching a critical stopping rule, the Investigator must also be contacted by phone.

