8.5 Safety Monitoring Rules

Stopping rules are described below in [Section 8.6](#).

Please refer also to the “Guidance for Investigator” section of the Investigator’s Brochure.

For the purposes of safety monitoring Baseline is defined as the average of the pre-dose test closest to Day 1 and the Day 1 value itself.

In addition to the standard monitoring of clinical safety parameters, the following guidelines are provided for the monitoring of selected parameters chosen based on preclinical and clinical observations.

In case of discrepancy between the test results from 2 sources, such as between the central and local lab, safety-mandated action must be initiated based on the more critical (lower or higher, as relevant) of the 2 values.

Confirmation Guidance: At any time during the study (treatment or post-treatment follow-up periods), the clinical laboratory results meeting any of the safety monitoring criteria presented below must be confirmed by performing measurements (ideally in the same laboratory that performed the initial measurement) on new specimens prior to administering the next dose of Study Drug (ISIS 678354 or placebo). All new specimen collections should take place as soon as possible (ideally within 3 days of the initial collection).

In addition, as described in [Section 6.2.1](#) hematology labs should be sent in parallel to the central and local laboratory for analysis.

Stopping Rule Guidance: The Investigator may interrupt or permanently discontinue study treatment for any medical reason including changes in clinical laboratory results.

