These alert levels are set to anticipate and prevent the risk of a medically significant change in renal function while receiving Study Drug. If any of the above criteria are met, treatment should immediately be interrupted, and the Study Medical Monitor should be informed. In addition, the result should be confirmed as soon as possible (as described in [Section 8.5](#)), but no later than 7 days after the initial event. If the confirmatory test is negative (i.e. repeat sample taken within 7 days is within normal limits), the patient may continue treatment upon consultation with the Study Medical Monitor.

The Investigator should also review the patient's concomitant medications for potentially nephrotoxic agents, and, with the results of these evaluations, review any decision to continue or discontinue the patient in consultation with the Study Medical Monitor and the medical area specialist consultant of the DSMB.

Further instruction regarding treatment interruption and/or permanent stopping of study drug can be found in [Section 8.6.2](#).

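### The SAP's 7-day confirmation window is shorter than the protocol's retest limit, so a timely normal retest on Day 8 or 9 is ignored and the abnormal value is reported as confirmed, chiefly for liver tests

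*Combined protocol and SAP*

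**What the plan says.** SAP 3.7.4 bases confirmation on "consecutive lab values performed on a different day to, but within 7 days", using central or local data. A second value that is the same or worse confirms the first. A better second value takes the first one's place for confirmation. If nothing falls in the window, the default applies: "If there is no retest within 7 days, then the initial value is presumed" confirmed. The SAP does not say whether the 7 days run from collection or from reporting.

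The protocol sets retest timing in several places:

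- **Section 6.2.1, any confirmatory or safety test:** at any time, "but no later than 7 days after the initial result is obtained".
- **Section 6.2.1, laboratory alerts:** these "should be received by them within 2 days from sample collection".
- **Section 8.5, confirmation guidance:** a new specimen before the next dose, as soon as possible, "ideally within 3 days of the initial collection".
- **Sections 8.5.2 and 8.6.2, renal tests only:** "but no later than 7 days after the initial event". Section 8.5.2 describes a negative confirmation as one where the "repeat sample taken within 7 days is within normal limits".

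Under the SAP, confirmed values feed the liver table that mirrors the stopping criteria, the renal abnormality table, an additional on-study platelet table, and the confirmed versions of the shift tables for eGFR, ALT, AST and total bilirubin.

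**The concern.** The two documents use the same number of days but not, on their wording, the same clock. The protocol counts from the result, and the SAP appears to count between tests. A site can meet section 6.2.1 and still have its retest treated as absent.

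Presuming confirmation is a sensible convention when nobody repeated the test. It gives the wrong answer when a timely repeat exists and is normal. Section 8.5 says that patients whose retest does not meet a stopping rule may in general continue dosing. Such a patient could be shown as a confirmed case in the liver table while having stayed on treatment because the same value was not confirmed. The confirmed tables are there to be more specific than the worst-value tables, and this default works against that purpose.

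**Working it through.** The plan states no figure to reproduce. The check is a day count.

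**Inputs**

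- Draw of the initial sample: Day 0.
- L, days from draw to result: 0 to 2 for an on-time central alert (protocol 6.2.1). Local laboratory reporting times are not given.
- Protocol limit: 7 days after the result (6.2.1).
- SAP window: a different day, within 7 days (3.7.4), read here as Days 1 to 7 after the draw.

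**Formula.** Latest compliant retest = Day L + 7. Uncovered days = Day 8 to Day L + 7, which is L days.

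| L | Latest retest under 6.2.1 | SAP limit | Uncovered days |
|---|---|---|---|
| 0 | Day 7 | Day 7 | 0 |
| 1 | Day 8 | Day 7 | 1 (Day 8) |
| 2 | Day 9 | Day 7 | 2 (Days 8, 9) |

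**Does another choice of start date close the gap?** Let the first sample take L1 days to report and the retest L2 days. For the latest compliant retest:

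- collection to collection: 7 + L1, up to 9 days;
- report to report: (L1 + 7 + L2) − L1 = 7 + L2, also up to 9 days;
- first report to second collection: 7 days.

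Only the last pairing agrees with section 6.2.1, and the SAP does not say that it is the one meant.

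**Does a routine sample fill the gap?** No. On treatment, "hematology samples will be collected every 14 days (± 2 days"), so the next one is due at 14 − 2 = Day 12 to 14 + 2 = Day 16. Liver tests follow the same interval for 3 months and are monthly after that. Neither falls inside either window.

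**Which outputs are exposed?**

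- *Liver.* No liver-specific outer limit applies to the first retest. Section 8.5.1 sends an initial elevation to section 8.5, and its weekly retesting starts only after confirmation. The exposed categories are aminotransferases above 8 x ULN, and above 3 x ULN with bilirubin, INR or symptoms. The category that requires persistence for 2 weeks is less exposed, because a normal value on Day 8 or 9 should break the persistence.
- *Platelets.* Table 3 asks for weekly counts from 75K to below 140K, every 2 to 3 days from 50K to below 75K, and daily below 50K. Only a weekly recheck that slips to Day 8 or 9 is exposed.
- *Renal.* The limit is 7 days after the initial event. If the event is the sample date, it equals the SAP window and there is no gap. If the event is receipt of the result, the same gap appears. The protocol does not say which.

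**Effect of one patient.** Each cohort has 25 patients randomized 4:1, so 25 × 4/5 = 20 active per group. Pooled placebo is 4 × 25 × 1/5 = 20. One wrongly confirmed patient adds 1/20 = 5 percentage points to a group's rate. For pooled active (4 × 20 = 80) it adds 1/80 = 1.25 points. This shows the cost per patient and does not estimate how many there will be.

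**The case against.** The strongest defence is that retests this late should be rare. Section 8.5 targets 3 days from collection and asks for confirmation before the next dose. This stands as to frequency. It does not remove the conflict, because the 3 days are an ideal, and the next dose can be 2 weeks away in Cohort C and 4 weeks away in Cohorts A and B.

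The defence can add that the error is conservative and visible. It can only overcount abnormalities. The shift tables for ALT, AST, bilirubin and eGFR are also produced on original values, all results including unscheduled ones are listed, and patients who actually stopped under the rules are tabulated separately. All of that stands and limits the harm. It does not make a refuted value a confirmed one.

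Four stronger readings are tempting, and the documents do not support them:

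- *That the renal table is equally affected.* Sections 8.5.2 and 8.6.2 set a separate limit that may match the SAP exactly.
- *That dose selection is distorted.* Protocol 10.1.4 refers to the incidence of platelet reductions, not confirmed ones, and the SAP's confirmed platelet table is additional to the worst-value table.
- *That 2 of 9 permitted days measures the error rate.* Retests are not spread evenly over the days, and 2 days is a target for receiving alerts, not an observed lag.
- *That the error differs between regimens because their dosing intervals differ.* This is plausible, but nothing in the documents shows it.

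**Conclusion.** The point holds in a limited form. SAP 3.7.4 has a window with no stated start date that, on its natural reading, is up to 2 days shorter than the retest limit in protocol 6.2.1. Its default then turns a compliant normal retest on Day 8 or 9 into a confirmed abnormality. The exposure is mainly in the confirmed liver table and the confirmed ALT, AST and bilirubin shift tables, and occasionally in the on-study confirmed platelet table.

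This rests on two assumptions: that the SAP counts from collection to collection (or report to report), and that central results take 1 or 2 days. With a same-day result there is no gap. With a result later than 2 days the gap is wider. The documents give no frequency; the number of patients may be zero and is probably small. No efficacy analysis and no unconfirmed worst-value table is touched. The rule is worth correcting because it gives a wrong answer in a case the protocol permits, but it does not threaten the trial's conclusions.

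**What to change.** In SAP 3.7.4:

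1. Name the start date. Use the next value of the same test, from either laboratory, on a different day and collected no later than 7 days after the date of the initial result.
2. Where no result date is available, use a stated window between collection dates. A 9-day window (2 + 7) assumes that the 2-day alert target was met, and the SAP should say so.
3. For renal values, keep the window consistent with protocol 8.5.2 and 8.6.2 once the initial event is defined. A general 9-day window could otherwise let a retest that is late under those sections overturn a renal value.
4. Presume confirmation only when no protocol-timely retest exists, and show presumed-confirmed patients separately from those confirmed by a second value.

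The protocol's retest limits in 6.2.1, 8.5, 8.5.2 and 8.6.2 start from different points (result, collection, event) and should be reconciled.

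The cost is a few sentences, one changed constant in the derivation and one flag, with no new data collected. The small downside is a slightly less conservative count of confirmed values, and the separate flag keeps the conservative figure recoverable.
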